2.0 Preliminary data

NCD incidence is high in SSA. We previously compared NCD incidence between a large urban U.S. setting (Nashville, TN) and a large urban African setting (Gaborone, Botswana). Standardized to an older, predominantly male U.S population, the overall NCD incidence rates were higher in Botswana (18.7 per 1000 PY).¹¹ Standardized rates differed most for cardiovascular events (8.4 vs. 5.0 per 1000 person-years) and non-AIDS-defining malignancies (8.0 vs. 0.5 per 1000 PY) - both higher in Botswana. This was one of the initial publications indicating that NCDs appeared to be a significant problem in our SSA setting and that monitoring, prevention, and treatment of NCDs should be a critical component of care in resource-limited settings.¹¹

Angiotensin receptor blocker (ARB) and ACEi exposure is associated with decreased all-cause mortality in HIV positive adults.⁸⁸ Adults (≥18 years of age) who achieved virologic suppression within 180 days of ART initiation and were from one of four North American AIDS Cohort Collaboration on Research and Design (NA ACCORD) sites were included. Primary analysis assessed the effect of time-varying ACEi/ARB exposure on all-cause mortality, using a marginal structural model to control for time-dependent confounders. Among 5252 participants, ACEi or ARB use was associated with significantly lower odds of death among HIV positive adults receiving suppressive ART when properly accounting for time-dependent confounding.⁸⁸

*Kidney disease is common among HIV positive adults presenting for care at AKTH.*¹¹⁰ 400 consecutive treatment-naïve HIV-positive patients with no other condition known to cause kidney disease were screened for proteinuria and eGFR. Kidney disease was found in 227 patients (56.8%), and proteinuria, including persistent microalbuminuria, was found in 211 (52.8%), with reduced eGFR (<60 mL/min/1.73m²) being identified in 64 persons (16.0%). Of note, the investigators biopsied a small series of patients (n = 20); among those with microalbuminuria, 2 of 5 (40%) had structural kidney disease in the form of collapsing FSGS (HIVAN). These findings confirmed that renal disease in HIV positive patients is high in Kano, Nigeria, and that microalbuminuria appears to be an important manifestation of collapsing FSGS.¹¹⁰

APOL1 influences albuminuria in young African American adults: [name] and [name] have published data from the CARDIA study ¹¹¹ (n=3,031) showing that the onset of *APOL1* kidney disease manifests as incident albuminuria and declining eGFR using serum cystatin C. Having *APOL1* HR genotypes was associated with a decline in eGFR only among those with albuminuria, compared to white adults (p=0.001).There were no differences in eGFR slopes for *APOL1* high-risk black adults without albuminuria or other blacks without albuminuria compared to the white adult reference group (**Figure 2**).¹¹¹

Table 1. APOLAmericans and I				the risk for	glomerula	ar disease among	g African
Percent	APOL1	risk genotype	es in black p	atients from l	J.S. and So	outh Africa (SA)	
US published case/control studies				S. Africa published studies (Kasembeli JASN 2015 ³⁰)			
	No.	OR [95% CI]	APOL1 HR	Ref	No.	OR [95% CI]	APOL1 HR
HIVAN	54	29 [13- 68.5]	72%	[name] ³⁶	38	89 [18-911]	78.9%
Primary FSGS	217	17 [11- 26]	72%	[name] ³⁶	18	3.1 [0.04-249]	5.6%
HIV POSITIVEFSGS	-			-	19	3.6 [0.2-42]	10.5%
HIVICK	-			-	28	6.2 [0.4-97]	20.0%
	US published biopsy studies				LEGEND: HIVICK (HIV-associated immune complex disease); HIVAN		
HIVAN	60	-	62%	Atta ³⁵	(HIV-as	(HIV-associated nephropathy) FSGS (focal segmental glomerulosclerosis). Population frequencies for carriage of APOL1 high-risk genotype: US ~ 14%, SA ~ 2-3%, Nigeria ~ 25%.	
HIV POSITIVEFSGS	35	-	63%	Fine ¹¹²	glomer frequer		
HIVICK	31	-	3%	Fine ¹¹²			

While the CARDIA population was largely HIV-negative, these data show that *APOL1* kidney disease presents early as albuminuria and supports our hypothesis that HIV interaction with *APOL1* high-risk status may be associated with worse outcomes in Nigerians with albuminuria (Aims 1 and 3).

APOL1 high-risk genotype is associated with glomerular disease among African Americans and black Africans in South Africa: In a series of published studies, [name] and [name]^{1,7-9,12,13} have shown that carriage of the *APOL1* HR genotype is strongly associated with primary FSGS and with HIVAN, with greater than 70% of individuals having these diagnoses possessing the *APOL1* HR genotype in the U.S. (Table 1). Interestingly, while the association for HIVAN was similar in African Americans (AA) and South African (SA) blacks, the enrichment of *APOL1* HR with primary FSGS (72%) in AA is strikingly higher compared to FSGS in SA blacks (5-10%) (Table 1). In a case-only biopsy series, we showed that the pathology of renal biopsies of HIVAN patients did not differ by *APOL1* genotype.⁶

Table 2. Selected relevant preliminary studies and data sources published by the project team				
Study/setting/country	Study Methodology	Key findings, lessons learned		
Comprehensive HIV and ART outcomes				
Pregnancy rates & birth outcomes among women on efavirenz (EFV)- containing ART, Botswana ([name] ¹¹³)	Prospective cohort	High pregnancy rates in women on EFV (7.9/100 person-years), indicating unmet need for family spacing services.		
Mortality with ART initiation in advanced HIV-1, Botswana ([name] ¹¹⁴)	Retrospective cohort	Significant clinical benefit with ART, even for advanced immunosuppression.		
Non-nucleoside reverse transcriptase inhibitor outcomes in Botswana ([name] ^{115,116})	RCT	Higher rates of treatment-modifying toxicities with nevirapine (NVP) (vs. EFV). NVP-treated women trended towards higher virologic failure with resistance vs. women on EFV.		
Risk factors for symptomatic hyperlactatemia and lactic acidosis among combination ART-treated adults in Botswana ([name] ¹¹⁷)	RCT	Higher rates of symptomatic hyperlactatemia/lactic acidosis in overweight (BMI>25) females		
Non-communicable diseases				
End stage renal disease among HIV positive adults in North America ([name] ³³)	Large, retrospective observational cohort	High rates of end stage renal disease among blacks		
Incidence rates of NCDs in a large U.S. center (Vanderbilt) versus a large African setting, Botswana ([name] ¹¹) Clinical Trials	RCT (Botswana) vs. retrospective observational data (U.S.)	Higher rates of age-standardized NCDs in Botswana		
	Cluster DCT	An integrated DMTCT neckage		
Determine the optimal means (intervention package) for prevention of mother-to-child HIV transmission (PMTCT) in Nigeria ([name]) ([name] ¹¹⁸)	Cluster RCT	An integrated PMTCT package significantly improved a) ART initiation (adjusted RR (aRR)=3.3 (1.4-7.8)] and b) 12 week maternal and infant retention in care (aRR = 9.1 [5.2-15.9] in rural Nigeria		
Stroke prevention in Nigerian children with sickle cell disease (SCD) trial (SPIN trial)	First NIH-sponsored sickle cell disease RCT in SSA	A hydroxyurea trial for children with SCD is feasible in SSA, but requires extensive capacity building		

Г

3.0 Inclusion/Exclusion Criteria

Inclusion and exclusion criteria to be used for participant enrollment into Study Aim 1 are shown below.

Inclusion criteria:

- 18-70 years of age
- HIV-positive (as documented by HIV-1 ELISA testing)
- On ART for a minimum of six (6) months

Exclusion criteria:

- Patients unwilling to consent to participate in this study
- On ART for < 6 months

Recruitment strategies:

NOTE: Although the eligible population of the HIV clinic at AKTH is 40% male, we anticipate that females will be more likely to enroll in this study, given our previous experience. Therefore, study staff will specifically target males for enrollment in order to achieve a gender balance in our study enrollment. Strategies that will be utilized by staff include use of male counselors in the clinic, utilization of male peer counselors for targeted recruitment, and extension of clinic hours to accommodate male participants who may not be able to attend otherwise due to work engagements. These strategies have all been utilized successfully by our team in previous studies and HIV scale-up efforts within Nigeria and Mozambique.¹¹⁸⁻¹²⁰ In addition, given preliminary Aim 1 data, with the mean duration of ART among enrolled aim 1 participants being > 8 years, strategies will be utilized by staff to prioritize the identification of persons more recently (within the past 6-24 months) in order to enroll a large cohort of HIV-positive adults with a more balanced duration of time on ART. Lastly, also given preliminary Aim 1 data review coupled with DSMB feedback (January 23, 2019), it was seen that ~ 75% of enrolled aim 1 participants (n = 380) had a self-reported ethnicity of Hausa/Fulani; with only \sim 4-5% self-reporting their ethnicity as Yoruba. Based on published literature to date^{39,40}, carriage of the *APOL1* high risk (HR) genotype has been shown to be highest among persons of Yoruba descent and other ethnic groups (i.e. lgbo) and more prevalent in the southern part of Nigeria. To address this in order to increase enrolment of persons of Yoruba descent, we will plan to open a second study site; namely the Infectious Disease Hospital that is also in Kano, as the demographics of the population this hospital serves is guite different when compared to AKTH in that they service significantly higher proportions of persons of Yoruba and other ethnicities from southern Nigeria; where proportions of the population possessing the APOL1 HR genotype are highest^{39,4039-40}.

Inclusion and exclusion criteria to be used for participant enrollment into Study Aim 2 are shown below.

Inclusion criteria:

- Participated in Study Aim 1: prevalence of *APOL1* high risk status and clinical correlates
- Suppressed plasma viral load result (≤ 20 copies/mL) within the past 6 months, and no unsuppressed viral load during that time. Routine viral load monitoring has only recently been implemented at AKTH. By enrolling only patients with recent evidence of viral suppression, we will reduce the impact of ongoing HIVassociated viral replication in non-adherent persons as a contributing cause of immune activation and therefore end-organ complications, including kidney disease.
- Completing Aim 1 of the study **AND** having a repeat single uACR value between 30-300 mg/g (based on first morning voided specimen) at time of Aim 2 screening to confirm eligibility.
- \leq 1+ hematuria on urine dipstick
- eGFR ≥ 60 ml/min/1.73m² based on serum creatinine value obtained during Aim 1 AND based on repeat serum creatinine value obtained at time of Aim 2 screening to confirm eligibility (NOTE: eGFR for Aim 1 and Aim 2 calculated using the CKD-EPI-Cr-CyC equation).

AND

• If female, non-pregnant (documentation of negative urine pregnancy test) and not breastfeeding/lactating. In addition, if female (with reproductive potential), needs to be reliably/consistently be receiving contraceptives (including documentation of being receiving reliable/consistent contraceptives; including enrolment in family planning/consultative services).

Exclusion criteria:

- eGFR of < 60 ml/min/1.73m²
- uACR < 30 mg/g or > 300 mg/g (on Aim 2 screening)
- K+ > 5.0 mmol/L, or reasons to be concerned about hyperkalemia
- History of diabetes mellitus (would qualify for treatment with an ACEi/ARB) [NOTE: Standardized diabetes screening procedure (fasting or random glucose ≥ 6.1 mmol/L)]
- ≥ 2+ hematuria on urine dipstick (assuming they might have glomerulonephritis from chronic active hepatitis B and/or C as both conditions can also cause albuminuria/proteinuria)
- Poorly controlled hypertension (Mean BP readings > 160/110 mm Hg in past 6 months)
- Persistent symptomatic hypotension (BP < 90/60 mm Hg) (on 2 or more successive readings)
- Known history of chronic congestive heart failure
- Initial screening uACR value > 300 mg/g plus urine dipstick ≥ 2+ for protein
- Currently receiving an ACEi and/or ARB;

OR

• Lack of suitability as a study candidate (i.e. active substance use disorder, active use of potentially nephrotoxic medication(s) [e.g. traditional medicines, etc.] and/or history of poor compliance [e.g. multiple missed scheduled clinic appointments, etc.])

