1.0 Rationale and Specific Aims

Nigeria is home to the fourth largest HIV-positive population in the world, having an estimated ~ 1,900,000 people living with HIV and 53,000 AIDS-related deaths annually.⁹⁸ Non-communicable diseases (NCDs), including kidney disease, among HIV-positive and HIV-negative adults in sub-Saharan Africa (SSA) represent a burgeoning epidemic. This study will be the first of its kind providing randomized controlled trial (RCT) evidence informing the optimal strategy to manage HIV-positive adults with albuminuria, particularly those with *APOL1* risk alleles who are genetically susceptible to kidney disease and potentially other life-threatening (i.e. cardiovascular) end-organ complications. Confirmation of the highest rates of adult HIV-positive populations globally carrying *APOL1* high-risk genotypes (~ 25%) would have significant implications for clinical care (including monitoring strategy) of persons in Nigeria and the West African region as a whole.

This study of HIV kidney disease is innovative for the following reasons:

1) Microalbuminuria among HIV-positive adults in Nigeria most likely represents underlying early structural kidney disease. This was the case in a small kidney biopsy series performed among HIV-positive adults presenting with persistent microalbuminuria in South Africa, of whom 6 of 7 were found to have HIV-associated nephropathy.⁸⁰ The present study will be the first to evaluate therapy to treat microalbuminuria in this population with the goal of preventing the progression of kidney disease.

2) *APOL1* variants are a major driver of kidney disease in HIV-positive persons. Most existing data on APOL1 risk variant prevalence are based on DNA from studies with very small sample sizes among specific African ethnic groups. This will be the largest genetic risk variant survey to date among individuals in West Africa, the region of the world with the highest documented carriage rates of the *APOL1* high-risk (HR) genotype.

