Specific Aim 1: To determine the prevalence of *APOL1* renal risk variants among 2,600 HIV-positive individuals in Nigeria and assess whether *APOL1* HR status correlates with prevalent albuminuria, eGFR, and/or prevalent CKD (defined as macroalbuminuria or eGFR <60 ml/min/1.73 m²) in this population.

Hypothesis: ~25% of those screened will carry the *APOL1* HR genotype, which will be associated with albuminuria, lower baseline eGFR, higher uACR, and higher rates of prevalent CKD.

Definitions: Microalbuminuria will be defined as having a mean uACR of 30-300 mg/g. CKD will be defined by the presence of proteinuria or an eGFR of < 60 ml/min/1.73m².

Study Population: We will determine the prevalence of *APOL1* risk variants in a large group of HIV-positive adults (n = 2,600) in Nigeria and correlate them with early markers of kidney disease; namely microalbuminuria, reduced eGFR, and CKD. All consecutively seen HIV-positive ART-experienced (6+ months) adults (\geq 18-70 years of age) presenting for care at AKTH will be approached for enrolment into this study. **NOTE**: We will be enrolling ART-experienced adults (on ART for 6+ months). Specifically, if on ART for 6-12 months, then subjects need to have a plasma viral load value < 20 copies/mL from their 6-month blood draw, and if on ART for > 12 months, then enrolled participants need to have a suppressed viral load result (i.e. < 20 copies/mL) on their most recent viral load blood draw---which needs to be within the past 6 months). Routine viral load monitoring has only recently been implemented at our study site in north-central Nigeria, and by enrolling only patients with recent evidence of viral suppression, we will do our best to eliminate ongoing HIV-associated viral replication in non-adherent persons as a potential contributing cause to immune activation and therefore NCD end-organ complications, including kidney disease.

1.2 Specific Aim 2

Specific Aim 2: To assess whether RAAS inhibition with an ACEi compared to placebo, significantly reduces incidence of albuminuria or reduced eGFR among 280 HIV-positive individuals with microalbuminuria who are receiving ART.

Hypothesis: After two years,

- A significantly higher proportion of participants in the intervention vs. SOC arm will regress from microalbuminuria to normoalbuminuria (uACR<30 mg/g); anticipated hazard ratio = 2.5.

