8.0 Statistical Considerations

[figure not shown]
Specific Aim 1

Sample size justification: A screening sample size of 2,600 participants will yield sufficient sample size for randomization in Specific Aim 2 detailed below. With 2,600 persons screened for Aim 1, the prevalence of *APOL1* renal risk variants may be estimated with precision (half-length of the 95% confidence interval) equal to 0.02 or better. Assuming a microalbuminuria prevalence of 17.5% based on recent data obtained from HIV-positive adults (n ~ 460) screened at AKTH,¹¹⁰ where this study will take place, we will have 90% power to detect a relative risk of microalbuminuria of 1.37 or higher in participants with renal risk variants compared to participants without, and we anticipate that 1 in 4 participants will have renal risk variants. We estimate, based on our experience with our studies at this site, that enrollment for Aim 1 will take 12 months. In addition to analyzing *APOL1* risk as a binary high/low risk status, we will also examine relative risk of microalbuminuria with *APOL1* risk categorized based on the presence of 0, 1, or 2 alleles, as this will lead to an increased understanding of the risk associated with the presence of a single risk allele.

Statistical analysis plan: We will estimate the prevalence and associated 95% confidence interval of *APOL1* renal risk variants. We will test whether the presence of these variants is associated with log₁₀uACR or eGFR using Wilcoxon rank sum test. Multivariable linear regression for each of log₁₀uACR or eGFR will be used to adjust for potential confounders, including: sex, age, CD4+ cell count, viral load, and the presence/absence of specific comorbid medical conditions (hypertension, cardiovascular disease, diabetes mellitus, etc.). For linear regression, appropriate transformations of dependent variables will be used to satisfy modelling assumptions. To relax linearity assumptions, covariates will be modelled using restricted cubic splines.¹³⁵ Modified

Poisson regression adjusted for similar variables, will be used to assess associations with prevalent CKD, microalbuminuria, and reduced eGFR (< 60 mL/min/1.73m²), and 95% confidence intervals.

Specific Aim 2 Sample size justification: We will

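### Aim 1 reports one pooled APOL1 high-risk prevalence although recruitment was redirected toward high-carriage ethnic groups, so the figure depends partly on the recruitment mix and its confidence interval does not show this

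*Combined protocol and SAP*

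**What the plan says.** Section 1.1 (Specific Aim 1, Study Population) sets the sampling frame: "All consecutively seen HIV-positive ART-experienced (6+ months) adults" attending the first hospital (AKTH) are to be approached. The hypothesis there is that about "25% of those screened will carry the" high-risk genotype. Section 1.0 attaches wider meaning to the result: "Confirmation of the highest rates of adult HIV-positive populations globally carrying" high-risk genotypes, at about 25%, is said to matter for care in Nigeria and in West Africa as a whole.

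Section 3.0 (Recruitment strategies) changes the frame. A review of the first 380 enrolees, with DSMB feedback, found about 75% Hausa/Fulani and about 4-5% Yoruba by self-report. The plan responds that "in order to increase enrolment of persons of Yoruba descent, we will plan to open a second study site", a second hospital in Kano. The stated reason is that this hospital serves far more Yoruba and other southern groups, in whom the high-risk genotype is most frequent.

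Section 8.0 (Specific Aim 1) was not changed to match. It says "We will estimate the prevalence and associated 95% confidence interval of" the risk variants, and "With 2,600 persons screened for Aim 1" it claims "precision (half-length of the 95% confidence interval) equal to 0.02 or better". It mentions no stratification, weighting or standardisation by ethnicity, site or recruitment period. The named adjustment covariates for the association models include neither ethnicity nor site. Section 5.0 lists race/ethnicity among the data collected. Sections 4.0 and 6.0 still name AKTH as the only place of enrolment.

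**The concern.** A prevalence estimate needs a population that it describes. Consecutive patients at one clinic provide one. Adding a site because its patients are more likely to carry the genotype means sampling on a variable that, on the plan's own account, predicts the quantity being estimated. The pooled proportion then moves with the number each site contributes, and a binomial interval around it gives no sign of this.

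The Background derives the expected 25% from risk-allele frequencies above 50% in Yoruba and Igbo people, and recruitment was then steered toward those and similar groups. If carriage is lower in Hausa/Fulani, which is the reason given for the change, enrichment pulls the pooled figure toward the hypothesised value. At stake is a headline descriptive result of Aim 1 and the use that Section 1.0 makes of it. The randomised comparison in Aim 2 is not affected.

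**Working it through.** **Inputs from the documents.** n = 2,600, expected prevalence 25% and half-width 0.02 or better (Section 8.0). About 75% Hausa/Fulani and 4-5% Yoruba among the first 380 (Section 3.0). Risk-allele frequency above 50% in Yoruba and Igbo (Background). With frequency 0.50 and Hardy-Weinberg proportions, two risk alleles occur in 0.50² = 25%.

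**Inputs not in the documents, assumed here.** Carriage in Hausa/Fulani, *h*: 5, 10, 15 or 20%. Carriage in everyone else: 25%. Final non-Hausa/Fulani share, *s*: 40% or 50%, against 25% in the first 380.

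**Step 1: the plan's precision.** Half-width = 1.96 × √(p(1−p)/n).
- p = 0.25: 1.96 × √(0.25 × 0.75/2,600) = 1.66 points.
- p = 0.50 (worst case): 1.92 points.

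The stated precision reproduces. The arithmetic is right, but it covers sampling error only.

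**Step 2: effect of the mix.** Pooled prevalence = (1−s) × h + s × 25%. The shift from s = 25% is (s − 0.25) × (25% − h).

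| h | Pooled, s=25% | Pooled, s=40% (half-width) | Shift | Pooled, s=50% (half-width) | Shift |
|---|---|---|---|---|---|
| 5% | 10.0% | 13.0% (1.29) | 3.0 | 15.0% (1.37) | 5.0 |
| 10% | 13.75% | 16.0% (1.41) | 2.25 | 17.5% (1.46) | 3.75 |
| 15% | 17.5% | 19.0% (1.51) | 1.5 | 20.0% (1.54) | 2.5 |
| 20% | 21.25% | 22.0% (1.59) | 0.75 | 22.5% (1.61) | 1.25 |

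Half-widths and shifts are in percentage points. At s = 25% the half-widths run from 1.15 to 1.57. The shift clearly exceeds the half-width in five of the eight enriched scenarios. It ties in one (1.50 against 1.51 at h = 15%, s = 40%) and is smaller in the two with h = 20%.

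**Step 3: change in share that moves the estimate by 1.66 points.** 1.66/(25 − h) gives 8, 11, 17 and 33 percentage points of share for h = 5, 10, 15 and 20%.

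**The case against.** Four points can fairly be made for the plan.

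- **The hypothesis is about the sample.** Section 1.1 words it for those screened, and Section 8.0 says "we anticipate that 1 in 4 participants will have renal risk variants". The pooled proportion answers that literally. This stands. The difficulty begins where Section 1.0 carries the figure to Nigeria and West Africa, and where the legend of Table 1 in Section 2.0 gives about 25% as a population frequency for Nigeria.
- **Enrichment is legitimate.** Section 5.0 plans about 35 two-allele participants in each of two randomisation strata, and Aim 3 depends on them. The change is also openly documented. This stands, and nothing here asks for recruitment to be reversed.
- **The size is unknown.** Section 3.0 only plans the site and gives no enrolment number. Hausa/Fulani carriage is not given. About 20% of the first 380 were neither Hausa/Fulani nor Yoruba, and treating them as 25% carriers is an assumption. This stands, so the table is a range and not an estimate.
- **AKTH alone does not represent Nigeria either.** This also stands. The AKTH mix is one possible standard, and nothing in the documents makes it the only test of the 25% hypothesis.

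A reader might infer that the second site decides whether 25% is confirmed. The scenarios do not show this. The highest is 22.5% with a half-width of 1.61, an upper limit of 24.1%, so all twelve pooled figures exclude 25% with or without enrichment. A reversal needs carriage above 25% in the enriched groups. For example, 30% there and 20% in Hausa/Fulani would give 22.5% at s = 25% and 25.0% at s = 50%. An allele frequency above 50% permits that, but the documents give no such carriage figure.

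A reader might also infer that patients at the second site are picked by ethnicity or not approached consecutively. Section 3.0 does not say so; the selection it describes is of the site.

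**Conclusion.** The concern holds as a mismatch between the sampling frame and the planned estimate. Recruitment is steered toward groups that the plan calls high-carriage, the analysis keeps one unweighted prevalence, and Section 1.0 generalises it. The pooled figure describes the enrolled sample, whose composition is partly a recruitment choice, and its interval leaves that out.

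Under the stated assumptions the shift is 0.75-5.0 points against a half-width of about 1.2-1.6. The direction is upward if carriage is lower in Hausa/Fulani, as the plan supposes. It would be wrong to say that the shift always matches the reported uncertainty, since it does not when Hausa/Fulani carriage is near 20%. Confidence is high in the mechanism and low in the size. The change should be made before the Aim 1 genotype results are analysed.

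**What to change.** In Section 8.0, Specific Aim 1:

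1. Report high-risk prevalence with a 95% confidence interval by self-reported ethnic group and by site (or before and after the second site opens).
2. Label the unweighted pooled figure as the prevalence in an ethnically enriched sample.
3. Base any statement about a wider population on a directly standardised figure, Σ wₖpₖ, with the weights wₖ taken from a named ethnic mix specified in advance. The AKTH clinic mix is one option. If the first 380 enrolees supply it, note that Section 3.0 also describes targeting men, so they may not be a clean consecutive sample.

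Reconcile the consecutive-patient wording in Section 1.1 and the AKTH-only wording in Sections 4.0 and 6.0 with Section 3.0.

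The cost is SAP wording and a weighted estimate from data already collected. The standardised interval may be somewhat wider than that of an unenriched sample of the same size. For example, take h = 10%, 25% in the rest, 1,300 enrolled from each, and known weights of 0.75 and 0.25. The half-width is 1.96 × √(0.75² × 0.09/1,300 + 0.25² × 0.1875/1,300) = 1.36 points, against 1.32 for a simple sample at 13.75%. Estimated weights, or a standard that gives heavy weight to a small group, would widen it further. The standardised figure may also lie further from 25%.
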